- Update the hypotheses to clarify that no formal hypothesis will be tested for safety endpoints, and added that a DRR is hypothesized to be consistent with results from the global phase 3 study
 - The hypothesis testing for DRR will be conducted on the first 18 treated subjects at dose level 1 if no dose de-escalation is required
- Update the Statistical Considerations, which included:
 - The primary efficacy analysis will occur when a durable response outcome has been assessed for all subjects
 - The analysis set was defined for dose de-escalation and no dose de-escalation
- Clarify that subjects may be included in the evaluation for both safety and efficacy
- Update the primary completion definition
- Update [Table 2](#). Schedule of Assessments, Tumor Assessments, to match the text
- Update the women not of childbearing definition to match other TVEC protocols
- Definition of DLT (dose limiting toxicity) was updated to match 20140318 study
- [Section 9.3](#)-Pregnancy and Lactation Reporting was updated to reflect new protocol template language
- Update Key Sponsor Contact

List of Tables

| | | |
|----------|--|----|
| Table 1. | Probability of Declaring a Cohort Safe or Unsafe | 9 |
| Table 2. | Potential Japanese Melanoma Phase 2 Single-Arm Designs to Test a Durable Response Rate Hypothesis Without Dose De-escalation | 10 |

List of Figures

| | | |
|-----------|---|----|
| Figure 1. | Probability of Declaring a Cohort Safe (Unsafe) | 9 |
| Figure 2. | The Definition of Analysis Sets | 14 |

List of Appendices

| | | |
|-------------|--|----|
| Appendix A. | Conventions for Clinical Data That Require Imputation for Partial or Missing Date | 24 |
| Appendix B. | Cutoff Values for qPCR Assay | 26 |

Table of Abbreviations

| Abbreviation or Term | Definition/Explanation |
|-------------------------------------|--|
| BRAF | serine/threonine protein kinase B-Raf V600E/K |
| CI | confidence interval |
| CR | complete response |
| CRF | case report form |
| CTCAE | Common Terminology Criteria for Adverse Events |
| DLRT | Dose Level Review Team |
| DLT | dose limiting toxicity |
| DNA | deoxyribonucleic acid |
| DOR | duration of response |
| DRE | Disease-related events |
| DRR | durable response rate |
| ECG | electrocardiogram |
| ECOG | Eastern Cooperative Oncology Group |
| End of Study for Individual Subject | The last day that protocol-specified procedures are conducted for an individual subject (ie, the date the subject withdraws full consent from the study, completes the safety follow-up visit or long-term follow-up [whichever is later] or death). |
| End of Study (primary completion) | The time when the last subject is assessed or receives an intervention for the purposes of final collection of data for the primary efficacy analysis. This will occur when a durable response outcome has been assessed for all subjects included in the primary efficacy analysis. |
| End of Study (end of trial) | The time when the last subject is assessed or receives an intervention for evaluation in the study. This is anticipated to occur when the last subject has had the opportunity to complete the safety follow-up visit or the last long term follow-up visit, whichever occurs later. |
| End of Treatment | The day of the last assessment for the protocol-specified treatment phase of the study for an individual subject |
| HCP | Health care providers |
| Heart rate | number of cardiac cycles per unit of time |
| HSV-1 | herpes simplex virus type-1 |
| ICH | International Conference on Harmonisation |
| IP | Investigational product |
| IPD | Important protocol deviations |
| LDH | lactate dehydrogenase |
| LTFU | Long term follow-up |
| ORR | overall response rate |
| OS | overall survival |
| PD | disease progression |
| PFS | progression-free survival |

| Abbreviation or Term | Definition/Explanation |
|----------------------|---|
| PFU | plaque-forming unit |
| PR | partial response |
| qPCR | real-time polymerase chain reaction |
| Source Data | Information from an original record or certified copy of the original record containing patient information for use in clinical research. The information may include, but is not limited to, clinical findings, observations, or other activities in the clinical trial necessary for the reconstruction and evaluation of the trial. Source data are contained in source documents (original records or certified copies). (ICH Guideline randomization identification, and stratification value. |
| TEAE | Treatment-emergent Adverse Events |
| TESAE | Treatment-emergent Serious Adverse Events |
| TTR | time to response |
| ULN | upper limit of normal |
| UE | unable to evaluate |
| vs | versus |
| WHO | World Health Organization |

1. Introduction

The purpose of this Statistical Analysis Plan (SAP) is to provide details of the statistical analyses that have been outlined within the protocol for talimogene laherparepvec Study 20140270 (**Amendment 5 dated 01 September 2020**). The scope of this plan includes the primary analyses for safety and efficacy and the final analysis that are planned and will be executed by the Biostatistics department unless otherwise specified.

2. Objectives

2.1 Primary

- To evaluate the safety and tolerability of talimogene laherparepvec, as assessed by incidence of dose limiting toxicities (DLTs), in subjects with unresectable stage IIIB-IV malignant melanoma
- These subjects will also be evaluated for the anti-tumor activity of talimogene laherparepvec as assessed by durable response rate (DRR) using modified World Health Organization (WHO) response criteria. DRR is defined as the rate of objective response (Complete response [CR] or partial response [PR]) lasting continuously for 6 months or greater and starting any time within 12 months of initiating therapy.

2.2 Secondary

- To evaluate the anti-tumor activity of talimogene laherparepvec, as assessed by overall response rate (ORR), time to response (TTR), duration of response (DOR), progression free survival (PFS) using modified World Health Organization (WHO) response criteria by investigators
- To evaluate overall survival (OS)

2.3 Safety

To evaluate the safety of talimogene laherparepvec as determined by subject incidence of adverse events and clinically relevant laboratory abnormalities where not defined as DLTs.

3. Study Overview

3.1 Study Design

This is a phase 1, multicenter, open-label study of talimogene laherparepvec in Japanese subjects with unresectable stage IIIB-IVM1c malignant melanoma that are candidates for intralesional therapy.

Approximately 18 subjects will be enrolled in the study. The DLT evaluation period is 35 days from the initial administration of talimogene laherparepvec. Initially, 6 DLT-evaluable subjects will be enrolled and treated at 100% of the dose regimen of talimogene laherparepvec (Dose 1) as described below. The first dose administered will be up to 4.0 mL of 10^6 PFU/mL (day 1, week 0) followed by dose of up to 4.0 mL of

10⁸ PFU/mL 3 weeks (+ 5 days) later. Subsequent doses of up to 4.0 mL of 10⁸ PFU/mL will be administered every 2 weeks (\pm 3 days) thereafter (see Protocol Section 6.2.1.1). A Dose Level Review Team (DLRT) meeting will be convened after 6 DLT-evaluable subjects are enrolled. Further enrollment will be temporarily paused until the DLRT meeting is convened and a decision is made on the dose level. Upon demonstration of safety based on DLT incidence < 33% in the first 6 subjects, an additional 12 subjects will be enrolled and treated at Dose 1 to obtain additional safety data.

However, if at any time there are 2 or more subjects with a DLT prior to enrollment of the first 6 DLT-evaluable subjects, an ad hoc DLRT meeting will be convened to determine if dose de-escalation is required.

The safety data during the enrollment of the additional 12 subjects will be monitored on an ongoing basis and an ad hoc DLRT meeting may be called, if needed, to determine the further course of the study.

Dose De-escalation

Following a decision to dose de-escalate, an additional 6 subjects will be treated at the lower dose regimen of talimogene laherparepvec (Dose -1). The initial dose administered will be up to 4.0 mL of 10⁶ PFU/mL (day 1, week 0) followed by dose of up to 4.0 mL of 10⁷ PFU/mL 3 weeks (+ 5 days) later. Subsequent doses of up to 4.0 mL of 10⁷ PFU/mL will be administered every 2 weeks (\pm 3 days) thereafter (see Protocol Section 6.2.1.2). The DLRT will review the safety data after the first 6 DLT-evaluable subjects at Dose -1 have been enrolled. Subject treatment will continue, however, further enrollment will be temporarily paused during the DLT review period to evaluate the 6 DLT-evaluable subjects at Dose -1. Upon demonstration of safety, additional subjects will be enrolled (up to a total of 18 subjects) at Dose -1 to obtain additional safety data.

The safety data of the subjects enrolled at the Dose-1 level will be monitored on an ongoing basis and an ad hoc DLRT meeting may be called, if needed, to determine the further course of the study.

All subjects will complete a safety follow-up visit approximately 30 (+7) days after the last dose of study treatment. Adverse events and disease related events will be collected as described in Protocol Section 9.2. After the safety follow-up visit, all subjects will enter the long-term follow-up. **If subjects receives therapy beyond 24 months after the last subject was enrolled in the study, when the LTFU period ends, they will not enter LTFU and their last vist will be safety follow-up visit. Otherwise,** subjects will be

[figure not shown]
followed for survival and subsequent anticancer therapies every 12 weeks (\pm 28 days) for approximately 24 months after the last subject is enrolled. In addition, talimogene laherparepvec related adverse events that occur **after the safety follow-up visit** through the end of the long-term follow-up will be reported. Maximum treatment duration is **48 months or until drug is commercially available in Japan**, total study duration of an individual subject can be up to around 4 years plus enrollment duration. The hypothesis test for DRR will include all subjects enrolled after dose de-escalation who received at least 1 dose of talimogene laherparepvec. If no dose de-escalation is needed, the DRR hypothesis test will include the first 18 subjects dosed.

3.2 Sample Size

Approximately 18 subjects will be enrolled. See protocol Section 10.2. The total number of subjects that will participate in the study and be used in the DLT analysis is approximately 18. The first 6 DLT-evaluable subjects will be used for the decision of dose de-escalation. If there is no dose de-escalation, the first 18 subjects in the safety analysis set will be used for the efficacy analysis of DRR, and the whole safety analysis set will be used for other efficacy analyses including ORR, TTR, DOR, PFS and OS. If dose de-escalation occurs, the efficacy analysis will be performed using the safety analysis set at Dose -1. In the current study design, a dose level will be considered safe if there are 0 to 1 DLTs observed in the initial 6 DLT evaluable subjects.

[Table 1](#) and [Figure 1](#) presents the probability of declaring a dose level safe (unsafe) for a range of true DLT rates for the protocol therapy for the 6 DLT-evaluable subjects (see triangle symbols). As shown below in [Table 1](#), the probability of declaring a dose level safe (unsafe) in the current study (based on only 6 DLT evaluable subjects) is 89% (11%), 42% (58%), and 11% (89%) if the true DLT rate is 10%, 30%, or 50%, respectively. Hypothetically, if the study were to enroll an additional 6 DLT-evaluable subjects after the initial 6 subjects (total of 12 DLT evaluable subjects), the probability of observing a DLT rate \geq 33% in the 12 subjects following the observation of 0-1 DLTs in the first 6 DLT evaluable subjects would be 0.6%, 8.6%, and 6.7% if the true DLT rate is 10%, 30%, or 50%, respectively.

Figure 1. Probability of Declaring a Cohort Safe (Unsafe)

DLT= dose-limiting toxicity; Pr = probability

Table 1. Probability of Declaring a Cohort Safe or Unsafe

| True Cohort DLT Probability | Probability Declare Cohort Safe | Probability Declare Cohort Unsafe |
|-----------------------------|---------------------------------|-----------------------------------|
| 10% | 89% | 11% |
| 20% | 66% | 34% |
| 30% | 42% | 58% |
| 40% | 23% | 77% |
| 50% | 11% | 89% |

DLT= Dose Limiting Toxicity

The total number of subjects that will participate in the study and be used in DLT analyses is approximately 18.

As shown in [Table 2](#), without dose de-escalation, 18 subjects provides maximum power to test the DRR null hypothesis in the range of 16 to 20 subjects, therefore only the first 18 subjects in the safety analysis set will be used in the analysis.

Table 2. Potential Japanese Melanoma Phase 2 Single-Arm Designs to Test a Durable Response Rate Hypothesis Without Dose De-escalation

| Null Hypothesis Durable Response Rate (DRR) | Alternative Hypothesis DRR | Target Significance Level | Target Power | Number of Evaluable Subjects | Minimum Number of Durable Responders (DRR) to Reject Null | Achieved Significance Level (Power) |
|---|----------------------------|---------------------------|--------------|------------------------------|---|-------------------------------------|
| 2% | 16.3% | 1-sided 5% | 80% | 16 | 2 (12.5) | 1-sided 4.0% (76.1) |
| | | | | 17 | 2 (11.8) | 1-sided 4.5% (79.1) |
| | | | | 18 | 2 (11.1) | 1-sided 5.0% (81.7) |
| | | | | 19 | 3 (15.8) | 1-sided 0.6% (61.9) |
| | | | | 20 | 3 (15.0) | 1-sided 0.7% (65.5) |

4. Study Endpoints and Covariates

4.1 Study Endpoints

4.1.1 Primary Endpoints

- Subject incidence of DLTs
- DRR using modified WHO response criteria by investigators

4.1.2 Secondary Endpoints

- ORR, TTR, DOR, and PFS using modified WHO response criteria by investigators
- OS

4.1.3 Safety Endpoints

Subject incidence of all the following, where not defined as DLT:

- adverse events
- grade \geq 3 adverse events
- serious adverse events
- clinically significant laboratory changes
- changes in vital signs

4.2 Planned Covariates

The following covariates will be used to examine efficacy and safety in subgroups or in multivariate analyses as appropriate:

- Grouped disease stage at baseline: IIIB-IVM1a vs IVM1b-c
- Line of therapy for current disease: 1st line vs 2nd line or later
- Dose level (Dose 1 vs Dose -1, if applicable)

5. Hypotheses and/or Estimations

No formal statistical hypothesis will be tested for safety endpoints in this trial. Based on the well tolerated safety profile from a global phase 3 study, it is hypothesized that talimogene laherparepvec will be safe and well tolerated in Japanese subjects with unresectable stage IIIB-IVM1c malignant melanoma.

A DRR is hypothesized to be consistent with results from the global phase 3 study ([Andtbacka et al., 2015](#)).

6. Definitions

1-year, 2-year survival

The Kaplan-Meier (K-M) estimate of the proportion of subjects alive at 1 year and 2 years from the first dose, respectively.

Actual Follow-up Time

Actual follow-up time for a subject is calculated from the first dose to the last on-study date (ie, death date, or date last known to be alive for patients still alive).

Baseline

Baseline in general refers to study day 1. The baseline value of a parameter (eg, vital signs, laboratory tests, and tumor measurement) is considered to be the latest value prior to receiving any study drug. If a subject did not receive study drug, then the latest value on or prior to the enrollment date is to be used.

Duration of Response (DOR)

DOR is defined as the time from the date of an initial response (CR or PR) to the earlier of PD or death. Subjects who have not ended their response at the time of analysis will be censored at their last evaluable tumor assessment.

Durable Reponse Rate (DRR)

DRR is the incidence of a durable response defined as an OR of CR or PR per modified WHO response criteria lasting continuously for ≥ 6 months and beginning at any point within 12 months of initiating therapy among a set of subjects analyzed. Subjects with an OR who do not have any follow-up tumor assessments will not be regarded as having a durable response.

Evaluable tumor assessment

An overall visit response other than UE.

Event of Interest (EOI)

MedDRA dictionary preferred terms for each EOI search strategy are defined and maintained by Amgen Safety Medical Coding.

Investigational product (IP)

Investigational product refers to talimogene laherparepvec in this study.

Objective Response (OR) per modified WHO criteria

Objective response will be assessed based on the response of the index lesions and nonindex lesions, and presence or absence of new lesions. Confirmation of complete or partial response is not required. The overall response is derived from time point response assessments as described in Protocol Tables 5, 6, 7.

Overall Response Rate (ORR)

ORR is defined as the incidence of an OR of CR or PR per modified WHO response criteria among a set of subjects analyzed. Subjects who do not have any follow-up tumor assessments will be regarded as non-responders.

Overall Survival (OS)

OS is defined as the interval from the first dose to the event of death from any cause; otherwise, OS is censored at the date the subject was last known to be alive.

Positive qPCR

By performing qPCR analysis, the talimogene laheparepvec DNA is \geq cutoff in the sample. Details are provided in [Appendix B, Section 12](#).

Potential Follow-Up Time

Potential follow-up time for a subject is calculated from the first dose to the analysis data cutoff date.

Progression Free Survival (PFS)

Progression-free survival (PFS) per modified WHO response criteria is defined as the interval from the first dose to the earlier of PD per modified WHO response criteria or death from any cause; otherwise, PFS is censored at the last evaluable tumor assessment.

Quantifiable qPCR

By performing qPCR analysis, the talimogene laheparepvec DNA is \geq LLOQ in the sample. Details are provided in [Appendix B, Section 12](#).

Study day

Study day is calculated from the first day when investigational product is administered to the subject; mathematically stated as Study day = (visit date – first dose date) + 1.

Study Day 1

Study day 1 is defined as the first day of administration of the investigational product after enrollment. The day prior to Study Day 1 is considered Study Day -1.

Study Week 0

The start of investigational product administration to the subject is study week 0. Study day 1 corresponds to the first day of study week 0.

Time to Response (TTR)

This endpoint will only be calculated for those subjects in the safety analysis set with CR or PR. It is defined as the time from first dose to the date of the first CR or PR.

Treatment period

Study day 1 through 30 days after the last administration of investigational product.

Treatment-emergent Adverse Events (TEAE)

Treatment-emergent adverse events are defined as any adverse event during the treatment period. Adverse events that occur on the same day as the first dose date of IP will be treated as treatment emergent events unless indicated otherwise (for example, if an event occurs on the same date as the first administration of talimogene laheparepvec and the check box indicating prior to the first dose of IP is checked on CRF, then the event will not be counted as a treatment-emergent emergent AE). Additionally, if an event is identified as disease-related on the eCRF, it will not be counted as a treatment-emergent AE).

Treatment-emergent Disease-related Events (TEDRE)

Treatment-emergent Disease-Related Events (DREs) are defined as adverse events, determined by the investigator to be disease-related, with an onset during the treatment period. DREs that occur on the same day as the first dose of IP will be treated as

treatment emergent events unless indicated otherwise (for example, if an event occurs on the same date as the first administration of talimogene laherparepvec and the check box indicating prior to the first dose of IP is checked on the eCRF, then the event will not be counted as a treatment-emergent DRE).

[figure not shown]
Treatment-emergent Serious Adverse Events (TESAE)

Treatment-emergent serious adverse events are defined as any serious adverse event with an onset date from first dose date to 90 days after the last dose of talimogene laherparepvec or 30 days following cessation of treatment if the subject initiates new anti-cancer therapy, whichever is earlier.

7. Analysis Subsets

The DLT analysis set will be used to summarize the subject incidence of DLTs for the study and the safety analysis set will be used for all other analyses of safety endpoints. The efficacy analysis will be conducted using the safety analysis set unless otherwise specified.

Figure 2. The Definition of Analysis Sets

7.1 DLT Analysis Set

The DLT analysis set will include DLT-evaluable subjects defined as subjects who had the opportunity to be followed for at least 35 days on treatment from the initial dosing (unless discontinued due to DLT) and received at least one dose of talimogene laherparepvec. Subjects may be replaced in a cohort if they are not evaluable for DLT (eg, a subject did not receive study treatment, or ended the study treatment before completion of DLT evaluation period for a reason other than experiencing a DLT).

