3.4 Replacement of Subjects

Subjects enrolled may be replaced if they are not evaluable for DLT (eg, a subject did not receive study treatment, or ended the study treatment before completion of DLT evaluation period for a reason other than experiencing a DLT).

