6.2.1.2 Dose-cohort Study De-escalation and Stopping Rules

6.2.1.2.1 Rules for DLT Evaluation

The DLT evaluation period is 35 days from the first dose of talimogene laherparepvec. To be evaluable for a DLT, subjects must have received at least 1 dose of talimogene laherparepvec and had the opportunity to be followed for the entire DLT evaluation period or have experienced a DLT within the DLT evaluation period. To obtain the first 6 DLT-evaluable subjects, subjects will be replaced if they are not evaluable for DLT (eg, a subject did not receive study treatment, or ended the study treatment before completion of DLT evaluation period for a reason other than experiencing a DLT).

A DLRT composed of the investigator(s), Amgen Medical Monitor, Amgen Global Safety Officer or designated safety scientist, Amgen Clinical Research Study Manager and Amgen Biostatistics representative will review data, monitor safety, and make dose and dose de-escalation decisions. Additional members may be added to the DLRT as needed (eg, Global Development Leader) (see [Section 10.3.2](#)). The DLRT will review the safety data after 6 DLT-evaluable subjects have been enrolled at Dose 1 (see below). Enrollment will be temporarily paused during the DLT review period to evaluate the 6 DLT-evaluable subjects. The decision to continue to enroll 12 additional subjects at the Dose 1 will be based on observing < 33% subject incidence of a DLT in the initial 6 subjects during the DLT evaluation period.

If at any time there are 2 or more subjects with a DLTs prior to enrollment of the first 6 DLT-evaluable subjects, an ad hoc DLRT meeting will be convened to determine if dose de-escalation (Dose -1) is required. The safety data during the enrollment of the additional subjects will be monitored on an going basis and an ad hoc DLRT meeting may be called, if needed, to determine the further course of the study.

Dose De-escalation

If dose de-escalation is needed, then the remaining subjects will be treated at the lower dose regimen of talimogene laherparepvec (Dose -1).

Dose	Initial dose	Subsequent doses
1	10^6 PFU/mL (day 1, week 0)	10^8 PFU/mL (3 weeks later and then every 2 weeks thereafter)
-1	10^6 PFU/mL (day 1, week 0)	10^7 PFU/mL (3 weeks later and then every 2 weeks thereafter)

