6.2.1.2.2 Definition of DLT

All toxicities will be graded using the CTCAE version 4.0 (see [Appendix A](#)). The occurrence of any of the following toxicities during the DLT evaluation period will be considered a DLT, if judged by the investigator to be related to the administration of talimogene laherparepvec:

- grade 4 non-hematologic toxicity
- grade 3 non-hematologic toxicity lasting > 3 days despite optimal supportive care
 - grade 3 fatigue will not be classified as DLT, irrespective of duration
- Any grade 3 or higher non-hematologic laboratory value reported as an adverse event if:
 - medical intervention is required, or
 - the abnormality leads to hospitalization, or
 - the abnormality persists for > 1 week (Laboratory values that persist for > 1 week but are deemed not clinically important per both investigator and sponsor will not be considered DLTs)
- Febrile neutropenia grade 3 or grade 4

- Thrombocytopenia $< 25 \times 10^9/L$ associated with bleeding event requiring intervention
- Serious herpetic event (eg, herpetic encephalitis, encephalomyelitis, or disseminated herpetic infection)
- grade 5 toxicity (ie, death)
- Any other intolerable toxicity leading to permanent discontinuation of talimogene laherparepvec

If a subject experiences a DLT during the DLT evaluation period, study treatment will be discontinued for that subject.

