10.1.1.4 Analysis Sets

10.1.1.4.1 DLT Analysis Set

The DLT analysis set will include DLT-evaluable subjects as defined in [Section 6.2.1.2.2](#).

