10.6 Safety Analyses

10.6.1 DLT Analysis

The subject incidence of DLT based on CRF will be summarized as a binary variable using the DLT Analysis Set by calculating the frequency, percentage, and exact 95% CI.

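### SAP 7.1 can leave out of the DLT analysis set a subject whose DLT the protocol's evaluability definition counts

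*SAP*

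**What the plan says.** **Protocol.** Section 6.2.1.2.1 sets the window: "The DLT evaluation period is 35 days from the first dose of talimogene laherparepvec". A subject who has received at least one dose is evaluable if they "had the opportunity to be followed for the entire DLT evaluation period or have experienced a DLT within the DLT evaluation period". Neither limb depends on why treatment ended. Section 6.2.1.2.2 defines the event by when it occurs and by relatedness: "The occurrence of any of the following toxicities during the DLT evaluation period will be considered a DLT", provided the investigator judges it related. Being on treatment at onset is not a condition.

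**SAP.** Section 7.1 requires at least one dose and that the subject "had the opportunity to be followed for at least 35 days on treatment from the initial dosing (unless discontinued due to DLT"). This adds an on-treatment condition and makes a single exception, tied to the reason for stopping.

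**Replacement example.** Protocol 3.4, Protocol 6.2.1.2.1 and SAP 7.1 all illustrate a non-evaluable subject as one who "ended the study treatment before completion of DLT evaluation period for a reason other than experiencing a DLT".

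**Use of the set.** DLT incidence is one of the two primary endpoints. SAP 10.6.1 summarises it "using the DLT Analysis Set by calculating the frequency, percentage, and exact 95% CI". SAP 3.2 states the decision rule: "a dose level will be considered safe if there are 0 to 1 DLTs observed in the initial 6 DLT evaluable subjects".

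**The concern.** The two documents give different answers for one kind of subject: dosed, stopped early for a recorded reason other than a DLT, and then affected by a related qualifying toxicity on or before day 35. Protocol 8.3.1 lists subject request, safety concern, protocol-specified criteria (a DLT or no injectable lesions, among others) and death as reasons for removal from treatment. The recorded reason can therefore be something other than DLT even though a DLT occurred. Two examples are a subject who stops at their own request and later has a serious herpetic event judged related, and a related fatal toxicity recorded simply as death.

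The protocol definition includes such a subject and the SAP wording leaves the subject out. With about 18 subjects, and a threshold between one and two DLTs in the first six, a single omitted event is visible in a primary result.

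**Working it through.** **1. The plan's own figures.** A dose is declared safe with 0 or 1 DLTs in 6, so P(safe) = (1−p)^6 + 6p(1−p)^5.

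| True DLT rate p | Calculated P(safe) | Stated (SAP Table 1, Protocol Table 4) |
|---|---|---|
| 10% | 88.6% | 89% |
| 20% | 65.5% | 66% |
| 30% | 42.0% | 42% |
| 40% | 23.3% | 23% |
| 50% | 10.9% | 11% |

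All reproduce. The issue is who is counted, not these probabilities.

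**2. The two definitions side by side** (every subject dosed at least once).

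| Subject | Protocol 6.2.1.2.1 definition | SAP 7.1, read literally |
|---|---|---|
| Stopped because of a DLT by day 35 | In | In |
| Stopped for another recorded reason, DLT by day 35 | In | Out |
| Stopped early for another reason, no DLT, could be followed to day 35 | In on the definition sentence; out on the replacement example | Out |
| On treatment to day 35, no DLT | In | In |

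The second row is the conflict. In the third row the protocol's own example pulls against its definition.

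**3. Does a kinder reading of the on-treatment condition remove the conflict?** SAP section 6 defines the treatment period as study day 1 through 30 days after the last administration. A second dose falls on day 22 to 27 (Protocol 6.2.1.1: no sooner than day 22, at most 5 days later), which carries the period to day 52 to 57. A subject given only the day 1 dose reaches day 1 + 30 = 31, short of 35. The gap shrinks to about four days in one-dose subjects but does not close.

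**4. Size for one such subject** (exact Clopper-Pearson 95% intervals).

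| Situation | Protocol definition | SAP 7.1, subject left out |
|---|---|---|
| First six, not replaced | 2/6 = 33.3% (4.3 to 77.7) | 1/5 = 20.0% (0.5 to 71.6) |
| First six, replacement has no DLT | 2/6 = 33.3% (4.3 to 77.7) | 1/6 = 16.7% (0.4 to 64.1) |
| Full set | 2/18 = 11.1% (1.4 to 34.7) | 1/17 = 5.9% (0.1 to 28.7) |

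**5. Direction across repeated trials (illustrative).** Let q be the fraction of DLT subjects dropped and r the fraction of non-DLT subjects dropped, with all of them replaced. The DLT rate among those kept is p(1−q) / [p(1−q) + (1−p)(1−r)]. The documents give neither q nor r.

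- With r = 0 this is p(1−q)/(1−pq). At p = 30%, q = 10% gives 0.27/0.97 = 27.8% and q = 20% gives 0.24/0.94 = 25.5%. The probability of declaring the dose unsafe moves from 58.0% to 53.2% and 47.9%. At p = 50% it moves from 89.1% to 86.4% and about 83%.
- With r = q the kept rate is exactly p, and 58.0% and 89.1% do not change.
- With r above q the kept rate exceeds p. For example, one DLT in six with one event-free early stopper dropped goes from 1/6 = 16.7% up to 1/5 = 20.0%.

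**The case against.** The strongest reply is that this is a narrow mismatch in wording with little bearing on the dose decision. Much of that stands.

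- **The dose decision.** A reader might infer that SAP 7.1 could by itself turn an intolerable dose into a safe one. The documents do not support that. The Dose Level Review Team decides under Protocol 6.2.1.2.1 and 10.3.2, reviews all available data, and may weigh grade 3 or higher toxicities that are not DLTs. The ad hoc trigger counts subjects with a DLT, without requiring them to be evaluable. The event would also remain in the safety analysis set. SAP 3.2 does tie the de-escalation decision to DLT-evaluable subjects, so the link is weak but not absent.
- **Direction.** A reader might infer that the SAP rule removes only events and so always flatters the dose. It does not: read strictly, it also drops event-free early stoppers, which pushes the rate the other way (step 5). The 53% to 48% and 86% to 83% figures need an unsourced q and the assumption that no non-DLT subject is dropped.
- **Time-based criteria.** A reader might extend the point to anyone who stops before a duration criterion is met. Protocol 6.2.1.2.2 already counts other intolerable toxicity leading to permanent discontinuation as a DLT. What remains is a stop for an unrelated reason during such a toxicity.
- **A generous reading.** The reference to opportunity could mean calendar time alone. The on-treatment words and the exception would then have no function, and the replacement example points the other way.
- **The example cannot override the definition.** It only illustrates a subject who is not evaluable, and a subject with a DLT is evaluable under Protocol 6.2.1.2.1. That is a fair reading of the protocol, but it does not repair SAP 7.1, whose own definition lacks the clause.

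SAP Figure 2, on the analysis sets, was not legible in the text available and might clarify the intent.

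**Conclusion.** The conflict holds in a limited form. Followed literally, SAP 7.1 can omit from a primary endpoint a DLT that Protocol 6.2.1.2.1 counts. The main effect is on the reported DLT incidence. One affected subject moves it from 2/6 to 1/5, or to 1/6 if the replacement has no DLT, and from 2/18 to 1/17 in the full set.

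This rests on a literal reading of the SAP exception, on a stop reason recorded as something other than DLT, and on the subject still being followed when the event occurs. No frequency can be put on the case from the documents, and no general direction of bias or loss of operating characteristics is claimed. A DLT recorded as the reason for stopping is treated alike in both documents.

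**What to change.** - **SAP 7.1:** replace the exception for subjects who discontinued due to DLT with *or experienced a DLT within the 35-day DLT evaluation period, regardless of the reason treatment ended*.
- **SAP 7.1, Protocol 3.4 and Protocol 6.2.1.2.1:** reconcile the replacement example with that definition by limiting it to subjects with no DLT in the evaluation period.
- **Protocol 10.1.1.4.1:** while editing, correct the cross-reference. It says "The DLT analysis set will include DLT-evaluable subjects as defined in" section 6.2.1.2.2, which lists the toxicities; the evaluability rule is in 6.2.1.2.1.

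The cost is wording. Adverse events are already reported through the safety visit 30 (+7) days after the last dose, and treatment-related events through the end of long-term follow-up (Protocol 9.2.2.1), so day 35 is covered even after a single dose for a subject still in follow-up. The downside is that the reported DLT rate may be slightly less favourable.
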